12.1.1. Primary Endpoint

The primary endpoint is an assessment of improvement in pelvic organ prolapse severity at 36 months as compared to Baseline.

12.1.1.1. Hypotheses

Superiority testing for effectiveness will be performed for the primary hypothesis.

Statistical testing will be performed to determine if composite endpoint of anatomic and symptomatic success rate in transvaginal mesh repair (treatment) group will be superior to traditional native tissue repair (control) group. The null hypothesis is that the success rate in treatment group is less than or equal to the success rate in control group:

$$H_0: \pi_{treatment} - \pi_{control} \leq 0$$

The alternative hypothesis is:

$$H_a: \pi_{treatment} - \pi_{control} > 0$$

where $\pi_{treatment}$ and $\pi_{control}$ is the probability of success in treatment group and control group respectively. The rejection of null hypothesis indicates the superiority of the treatment group over the control group.

Statistical testing will be performed to determine if the overall complication rate (i.e. serious adverse device effects and serious procedure-related adverse events) of treatment group is non-inferior to the control group. The null hypothesis is that the complication rate in treatment group is greater than or equal to the rate in control group plus margin:

$$H_0: \pi_{treatment} - \pi_{control} \geq \Delta$$

The alternative hypothesis is:

$$H_a: \pi_{treatment} - \pi_{control} < \Delta$$

where $\pi_{treatment}$ and $\pi_{control}$ are the overall complication rate in treatment group and control group respectively, and $\Delta > 0$ is defined as the non-inferiority margin.

12.1.1.2. Sample Size

The statistical power calculation is based on a superiority assumption with a binary primary outcome. Success, based on a composite endpoint of anatomic and symptomatic success at 36 month is assumed to be 70.0% for the native tissue arm and 85.0% for transvaginal mesh arm.¹⁷⁻²¹ With 2-sided type I error of 0.05 and type II error of 0.1 (power 90%), 316 subjects (158 subjects per arm) are needed to detect 15% difference of transvaginal mesh to native tissue repair. In addition to a superiority assumption, statistical testing will be performed for non-inferiority using a margin of -12%.

To assess for safety, the overall complication rate (i.e. serious adverse device effects and serious procedure-related adverse events) is anticipated to be approximately 14%.²² With type I error of 0.05 and type II error of 0.20 (power 80%), 298 subjects (149 subjects per arm) are needed to detect non-inferiority with a margin of 10%.

To assess for office-based interventions for complications, the rate is anticipated to be approximately 2%.²² With type I error of 0.025 and type II error of 0.10 (power 90%), 330 subjects (165 subjects per arm) are needed to detect non-inferiority with a margin of 5%.

To assess for of surgical intervention for complications, the rate is anticipated to be approximately 1%.²² With type I error of 0.025 and type II error of 0.10 (power 90%), 260 subjects (130 subjects per arm) are needed to detect non-inferiority with a margin of 4%.

Non-surgical subjects will be enrolled by the PFD Registry and analyzed in this clinical study. Non-surgical subjects will not be enrolled into this clinical study. Using the above calculations and assuming a 20% loss to follow-up rate, a total of 414 subjects (207 per study arm) will be enrolled to achieve the primary endpoint of success at 36 months.

12.1.1.3. Statistical Methods

For the primary efficacy endpoint, the comparisons of mesh repair to native tissue repair will be based on a two-sided 95% confidence interval for the treatment difference (mesh minus native tissue repair). If the entire confidence interval is above zero, superiority of mesh repair to native tissue repair will be demonstrated. The confidence interval will be calculated based on the pooling of treatment differences across propensity score strata for a binary endpoint, as described in Section 12.2.3 (Propensity Score Methodology).

If any data on the primary efficacy endpoint is missing, multiple imputation will be performed in which the missing values will be imputed five times under a logistic distribution model, using a fully conditional specification that includes the treatment arm and the assessments of the treatment success endpoint at each of 2, 6, 12, 18, and 24 months. As a sensitivity analysis, the comparison of treatments will also be performed using the following methods:

- Tipping point analysis
- Available cases only (i.e., only the subjects for whom the endpoint was assessed)

For the primary safety endpoint, the proportions will be calculated using for the numerator the number of subjects with an endpoint event and for the denominator the number of subjects in the analysis population (ITT and per protocol group). Non-inferiority will be evaluated using a two-sided 90% confidence interval for the treatment difference (mesh minus native tissue repair). If the entire confidence interval is below the margin (10%), non-inferiority will be demonstrated. The confidence interval will be calculated based on the pooling of treatment differences across propensity score strata for a binary endpoint, as described in Section 12.2.3 (Propensity Score Methodology).

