12.2.3. Propensity Score Methodology

Analyses comparing the treatment groups will be adjusted for the propensity score. The propensity score is the probability that the subject enrolled in the mesh arm rather than the native tissue (control) arm, given the characteristics of the subject and center. The characteristics identified are as follows: age, race, body mass index, smoking, diabetes, post-menopausal, prior prolapse repair, prior hysterectomy, estrogen use, POP-Q C measurement, POP-Q Ba measurement, POP-Q Bp measurement, concomitant repair for stress urinary incontinence, and surgeon case volume. Logistic regression of both treatment arms (i.e., (transvaginal mesh repair vs. native tissue repair) on these characteristics will be used to estimate the propensity score. The subjects will then be partitioned into five strata

corresponding to quintiles of the propensity score. If the balance between treatment arms within the strata is deemed adequate, the treatment difference adjusted for propensity score stratum will be estimated as described in the following.

The propensity adjusted treatment difference will be based on averaging the treatment differences of the propensity score strata. For a binary outcome, the within-stratum treatment difference is $D_j = p_{Tj} - p_{Cj}$, where p_{Tj} and p_{Cj} is the proportion of treatment and control subjects, respectively, in stratum j . The variance of D_j is approximately

$$V_j = \frac{p_{Tj}(1 - p_{Tj})}{n_{Tj}} + \frac{p_{Cj}(1 - p_{Cj})}{n_{Cj}}$$

Denoting the number of subjects in stratum j by $n_j = n_{Tj} + n_{Cj}$, the treatment difference will be estimated by the (weighted) mean of the within-stratum treatment differences

$$D = \sum_j \frac{n_j}{n} D_j$$

where $n = \sum_j n_j$ is the total sample size across all strata and study arms. D is approximately normally distributed with variance

$$V = \sum_j \left(\frac{n_j}{n}\right)^2 V_j$$

from which a confidence interval for the true treatment difference will be constructed. For each continuous outcome, the confidence interval will be constructed similarly, with D and V obtained as above with the treatment difference within each stratum replaced by $D_j = \bar{X}_{Tj} - \bar{X}_{Cj}$, where \bar{X}_{Tj} and \bar{X}_{Cj} , respectively, is the mean of the treatment and control subjects, and

$$V_j = \frac{S_{Tj}^2}{n_{Tj}} + \frac{S_{Cj}^2}{n_{Cj}}$$

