12.3.8.2. Statistical Methods

The comparisons of mesh repair to native tissue repair will be based on a two-sided 90% confidence interval for the treatment difference. The confidence interval will be calculated based on the pooling of treatment differences across propensity score strata for a binary endpoint, as described in Section 12.2.3 (Propensity Score Methodology).

Missing 12 month data for the composite efficacy endpoint will be handled by multiple imputation under a logistic regression model using a fully conditional specification. The imputation model will include treatment group and primary efficacy outcome at 2 and 6 month. A total of 5 imputed data sets will be generated.

The following methods will also be used as sensitivity analyses:

- Observed data only
- Tipping point analysis

12.3.9. **Justification of Pooling**

The analyses will be presented using pooled data across institutions. For each group, an analysis of the poolability will be made using logistic regression for binary outcomes, or analysis of variance for continuous outcomes, to assess differences between study institutions and to justify pooling data across institutions. Centers with less than 5 ITT patients may be combined.

12.3.10. **Multivariable Analyses**

For each treatment group, univariate and multivariate analyses will be performed to assess possible predictors of the improvement in pelvic organ prolapse at 36 month, mesh-related complications and subject reported outcomes. Possible predictors may include, but not limited to, demographic/baseline data and risk factors data. Factors from the univariate model with $p \leq 0.20$ will also be put into multivariate model using a stepwise procedure in a

logistic regression model. The significance thresholds for entry and exit into the model will be set to $p < 0.10$. Analysis of Covariance (ANCOVA) will be performed for subject reported outcome with appropriate predictors.

13. Data Management

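### The imputation models for the effectiveness composite leave out the propensity stratum over which the estimate is averaged, and use only five imputations

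*Combined protocol and SAP*

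**What the plan says.** **Estimator.** Section 12.1.1.3: "The confidence interval will be calculated based on the pooling of treatment differences across propensity score strata for a binary endpoint". Section 12.2.3 forms the strata from quintiles of the score ("The subjects will then be partitioned into five strata") and adds: "The propensity adjusted treatment difference will be based on averaging the treatment differences of the propensity score strata". The weights are n_j/n.

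**Imputation at 36 months.** Section 12.1.1.3: "the missing values will be imputed five times under a logistic distribution model". The predictors it lists are the arm and the success result at every earlier visit from month 2 to month 24.

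**Imputation at the 12-month interim.** Section 12.3.8.2: "The imputation model will include treatment group and primary efficacy outcome at 2 and 6 month". Here too the number of imputed data sets is five.

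Neither list names the propensity score, the stratum or any baseline covariate. Neither section fixes a random seed or names the rule for combining the imputed data sets.

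**Sensitivity analyses.** Section 12.1.1.3 lists a tipping point analysis and "Available cases only (i.e., only the subjects for whom the endpoint was assessed"). Section 12.3.8.2 lists the same two kinds.

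**Safety.** Section 12.1.1.3 divides the subjects with an event by all subjects in the analysis population. It describes no imputation.

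**The concern.** The analysis conditions on a variable that the imputation model does not contain. Two women in the same arm with the same earlier outcomes receive the same imputed probability of success, even if they sit in opposite quintiles of the propensity score. The plan itself treats the stratum variables as risk factors: section 12.2.2 gives their imbalance as the reason for stratifying, and section 12.2.3 includes baseline POP-Q points and prior prolapse repair among them. If they predict the outcome, the imputed values carry some of the between-arm imbalance back into each stratum.

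At stake is the primary superiority claim, which is decided by whether one confidence limit lies above zero. The interim tests are exposed in the same way, and the footnotes to section 12.3.8 tie them to a premarket application. Their model has only two earlier outcomes to draw on. The missing fraction may also exceed the planned loss to follow-up, because section 11.4.5 allows telephone visits with mailed questionnaires, which cannot supply the POP-Q part of the composite.

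**Working it through.** **Inputs from the documents.** Success 70% and 85%, two-sided 0.05, 90% power, 158 per arm, 20% loss, 207 per arm (12.1.1.2); 165 evaluable per arm (8.1); five strata (12.2.3); five imputations (12.1.1.3, 12.3.8.2).

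**Inputs assumed.** The crude-minus-adjusted gap, the share of mesh subjects by stratum, the within-subject correlation, the dropout pattern, the missing-information fraction (FMI), and Rubin's rules for combining.

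**1. The plan's own figures.** (1.960 + 1.282)² × (0.70×0.30 + 0.85×0.15) / 0.15² = 157.6, so 158 per arm. 165 / 0.80 = 206.25, so 207 per arm. Both reproduce.

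**2. Bound on the pull.** Let a fraction f be missing in each arm, unrelated to stratum, and let earlier outcomes carry no information about stratum. Imputed values in every stratum then have the arm's overall success rate, so stratum j contributes (1 − f)·D_j + f·D_crude. Averaging with weights n_j/n gives

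D_MI = (1 − f)·D_adj + f·D_crude, so the pull is f × (D_crude − D_adj).

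| Assumed gap (points) | f = 10% | f = 20% (planned) | f = 30% |
|---|---|---|---|
| 2 | 0.2 | 0.4 | 0.6 |
| 5 | 0.5 | 1.0 | 1.5 |
| 10 | 1.0 | 2.0 | 3.0 |

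**3. Simulated pull.** Set-up: 600,000 subjects, five strata with mesh shares from 20% to 80%, monotone dropout reaching 20% at month 36, sequential logistic imputation, and a within-subject correlation parameter of 0, 0.3, 0.6 or 0.8. Entries are points of bias against the full-data stratified estimate.

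| Gap | 0.20 × gap | Stratum omitted | Stratum included | Available cases, stratified |
|---|---|---|---|---|
| about 3 | 0.6 | 0.15 to 0.62 | 0.02 to 0.18 | 0.03 to 0.10 |
| about 6 | 1.2 | 0.46 to 0.98 | −0.08 to 0.18 | −0.01 to 0.10 |
| about 12 | 2.4 | 0.79 to 1.94 | −0.04 to 0.06 | −0.06 to 0.06 |

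Simulation noise is about 0.2 points. The pull is generally smaller when the correlation is stronger.

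**4. Noise from five imputations.** The complete-data SE at 207 per arm is √(0.3375/207) = 4.04 points. With between-imputation variance B = FMI × SE² / (1 − FMI), the Monte Carlo SD of the difference is √(B/m).

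- FMI 0.10: 0.60 points at m = 5, 0.19 at m = 50.
- FMI 0.20: 0.90 points at m = 5, 0.29 at m = 50.

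**5. Effect on the conclusion.** Set-up: 400 trials of 414 subjects, gap of 6 points favouring mesh, stratum omitted, simulated FMI about 0.19.

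| True difference (points) | SD of lower 95% limit over seeds, m = 5 / m = 50 | Two seeds disagree on superiority, m = 5 / m = 50 |
|---|---|---|
| 0 | 1.34 / 0.38 | 1.4% / 0.5% |
| 9 | 1.34 / 0.37 | 11.1% / 2.5% |
| 15 (planned) | 1.24 / 0.34 | 5.3% / 1.5% |

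The m = 50 disagreement rates rest on one pair of seeds per trial (2, 10 and 6 of 400).

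In the same trials with m = 5, superiority was declared with the stratum omitted and included in 2.25% and 1.75% under no effect (Monte Carlo error about 0.7 points), and in 92% and 85.5% at the planned effect.

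**The case against.** Much of the case on the other side stands.

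- **Earlier outcomes carry stratum information.** Each woman's own results at up to five visits are in the 36-month model, so her imputed value is not simply the arm average. This is why the simulated pull mostly falls below the bound.
- **The gap is unknown.** A 10-point gap would be two thirds of the planned 15-point effect, which is severe confounding. At about 3 points the simulated pull is 0.15 to 0.62 points.
- **A prespecified check exists.** The available-case analysis imputes nothing. Section 12.2.3 says that between-group analyses are propensity-adjusted, so it can be read as stratified, and it would then avoid this pull. It remains a sensitivity analysis, however, and its estimator is not stated where it is listed.
- **The model list might not be exhaustive.** The wording permits that reading, but a prespecified primary analysis should not depend on it.
- **Rubin's rules allow for a finite number of imputations.** Five cost precision and reproducibility; they do not make the interval invalid.

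A reader might infer that the confounding adjustment is undone, that the false-positive rate is inflated, or that the seed decides the result. The material supports none of these. Only a fraction of the gap returns, and it may favour either arm. Rejection under no effect was 2.25% against 1.75%, within simulation error. Seeds seldom disagree away from the boundary. Nor is the propensity score the only guard against bias: section 12.2.2 also assigns most centers to a single arm and documents those decisions before enrollment.

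**Conclusion.** The point holds as a moderate, easily removed defect in the effectiveness analysis at 36 months and at the interim. The pull toward the crude difference is bounded by about f times the gap, provided that missingness is unrelated to stratum and similar in the two arms. Its sign cannot be known in advance. The interim model, with fewer earlier outcomes, may sit nearer its bound; this was not simulated. The confounding gap, dropout pattern and correlation are assumptions, so the sizes are illustrations and not predictions for this trial. The noise from five imputations is small beside the SE but large enough to change a close call. The primary safety comparison is unaffected.

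**What to change.** 1. Add the propensity stratum as a categorical predictor, or the propensity score and its covariates, to the imputation models in sections 12.1.1.3 and 12.3.8.2. Section 12.2.2 already has the propensity work done blind to outcomes and before any endpoint analysis, so the strata exist when imputation is run.
2. Raise the number of imputations to at least 50 in both sections, prespecify the seed and name the combining rule.
3. State that the available-case analysis (12.1.1.3) and the observed-data analysis (12.3.8.2) use the same propensity-stratified estimator, so that they serve as a direct check on the imputed result.

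The cost is a few lines of SAP wording and minutes of computing. No new data and no design change are needed.

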10.2.3. Lost to Follow-up

Before a subject may be considered lost to follow-up the Investigator must make the following attempts to contact the subject:

- Two documented telephone attempts
- One certified letter

If the subject is able to be reached and no longer wishes to participate in the study the Investigator shall document the reason for the withdrawal and complete End of Study Case Report Form. If the subject is not able to be reached after the required attempts to contact the

subject are made and the subject has missed two consecutive follow-up visits within a 12 month calendar period, the subject may be considered lost to follow-up. The Investigator should document in the subject's medical record the attempts to contact the subject and reason for the withdrawal.

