10.2.5. Documentation of Early Termination

Once a subject withdraws from the study, the Case Report Form will be completed as appropriate up to the point of withdrawal and all Adverse Events shall be closed or documented as appropriate. Withdrawn subjects (who had the study procedure initiated) will be included in the Intent-to-Treat analysis and will not be replaced.

11. Study Methods

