11.4.5. Follow-Up

Subjects will be scheduled for follow-up visits as outlined in Table 11.1-1 (Data Collection Schedule). The follow-up visit schedule begins from the day the subject is discharged (e.g. leaves hospital/clinic) post-procedure and includes visit windows (counted in calendar days). Every effort should be made to do the follow-up visit within the window; however, if this is not possible, the site should attempt to complete the visit as soon as possible but before the next visit window opens. Follow-up visits will be considered missed once the visit window for the next follow-up visit opens. For the Month 36 visit, the visit is not considered missed until the last day of the visit window.

Every effort should be made to conduct the follow-up visit at the study site location. However, if the subject cannot physically return to the site for any reason, the follow-up visit may be conducted at the subject's home with their consent and if allowed by local institutional policy and the IRB/EC. If a home visit is not possible, every effort should be made to conduct as much of the visit as possible by phone (i.e., assess adverse events, risk factors, and analgesic intake) and to send the subject questionnaires by mail for completion.

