12.2. General Statistical Methods

12.2.1. Analysis Sets

The Intent-to-Treat (ITT) subject population includes all subjects who provide written informed consent to be enrolled into the study and have a surgery initiated (i.e. incision in vagina) regardless of their adherence with the entry criteria, regardless of treatment and withdrawal/protocol deviations.

The treated population includes all subjects who undergo a study surgical procedure. The subject is defined to have successfully completed the surgical procedure (i.e. prolapse repair successful) and discharged.

The Per Protocol (PP) population includes all subjects in the ITT Population who received the assigned treatment and had no major protocol deviations.

All primary and secondary endpoints will be analyzed on the ITT Population. The primary safety and non-safety endpoints will also be analyzed on the per-protocol population.

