19.2.1. Mesh Exposure and Erosion Event Classification

Assessment of mesh exposure and/or erosion will occur at all follow-up visits with pelvic examinations performed at 2, 6, 12, 18, 24, and 36 Months post-procedure. Identification of mesh exposure and/or erosion will occur by the medical staff member performing the pelvic exam and will be documented as an adverse event on the Case Report Forms.

19.3. *Risks Associated with Participation in the Clinical Study*

There are no additional risks with participation in this clinical study outside of the anticipated risks (see Section 19.2) for pelvic organ prolapse as conducted according to standard of care procedures.

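### The co-primary safety analysis counts subjects lost without a recorded event as event-free to 36 months, which can push false non-inferiority above the nominal 5%

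*Combined protocol and SAP*

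**What the plan says.** Section 7.1 defines the co-primary safety endpoint as serious device or procedure complications from baseline to 36 months. Section 12.1.1.3 takes the number of subjects with an event and uses "for the denominator the number of subjects in the analysis population (ITT and per protocol group"). Non-inferiority holds if a two-sided 90% interval for mesh minus control lies wholly below 10 points.

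Section 10.2.5 fixes who is in that denominator: "Withdrawn subjects (who had the study procedure initiated) will be included in the Intent-to-Treat analysis and will not be replaced". Section 12.2.1 defines the second set without a follow-up requirement: "The Per Protocol (PP) population includes all subjects in the ITT Population who received the assigned treatment and had no major protocol deviations".

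Loss is expected. Section 12.1.1.2 sizes the study "assuming a 20% loss to follow-up rate, a total of 414 subjects". Section 8.1 plans for 330 subjects in the 36-month safety analysis, while the rule divides by all ITT subjects, about 414.

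In Section 12.1.1.3, multiple imputation is tied to the efficacy endpoint, and the tipping-point and available-case analyses follow from it. The interim plan in Section 12.3.8.2 has the same structure: "Missing 12 month data for the composite efficacy endpoint will be handled by multiple imputation". Neither section states a missing-data method for safety.

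**The concern.** Events recorded before a subject leaves are counted, and events after she leaves are not. Her unobserved time is treated as observed and event-free. If both arms miss the same number of events, the difference is unchanged. If mesh misses more, the difference shrinks, and in a non-inferiority test shrinkage favours the claim.

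Mesh misses more when loss is about equal or higher in mesh and part of its excess risk comes late. Late mesh events are possible: "Assessment of mesh exposure and/or erosion will occur at all follow-up visits", that is, out to Month 36. The documents do not say how many of these would be serious. Loss could differ by arm, because treatment is not randomized and many centers may enroll only one arm (Sections 8.2 and 12.2.2).

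One of the study's two co-primary conclusions rests on this rule, and it has no planned check for missing follow-up. The efficacy conclusion has two.

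**Working it through.** **The plan's own figures.** Inputs from Section 12.1.1.2: 14% in both arms, margin 10 points, type I error 0.05, power 80%.

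n per arm = (1.645 + 0.842)² × 2 × 0.14 × 0.86 / 0.10² = 148.9, so 149 per arm and 298 in total. This matches the plan. For enrolment, 165 / 0.80 = 206.25, so 207 per arm, which also matches.

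**Size of the rule with no loss.** Take the margin as the truth: control 14%, mesh 24%, 207 per arm. Enumerating both binomials exactly and applying p_T − p_C + 1.645 √[p_T(1−p_T)/207 + p_C(1−p_C)/207] < 0.10 gives false non-inferiority of 5.2%.

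**Effect of loss.** Let L be the proportion lost in an arm and f the share of lost subjects' events that would fall after they leave. The recorded rate is p(1 − L f). With the same f in both arms, the recorded difference in points is 10 − f(24 L_T − 14 L_C).

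- Equal 20% loss, f = 0.5: 24 × 0.9 − 14 × 0.9 = 21.6 − 12.6 = 9.0 points, and false non-inferiority is 8.8%.
- Equal 20% loss, f = 0.25 and f = 1: 9.5 and 8.0 points, giving 6.8% and 14.7%.
- The bias vanishes when 24 L_T = 14 L_C, that is, when control loss is 24/14 = 1.71 times mesh loss.

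**Adding explicit timing.** Event times are assumed Weibull with shape 1 (constant hazard), 0.5 or 0.25 (increasingly early), scaled to 24% and 14% at 36 months. Loss is non-informative and uniform over 36 months (spread) or over 12 months (year 1).

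Example: constant hazard, spread 20% loss. With H = −ln(1 − p), the mean risk by the time of loss is 1 − p/H.

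- Mesh: H = 0.2744, mean risk 0.1255, recorded rate 0.8 × 0.24 + 0.2 × 0.1255 = 21.71%.
- Control: H = 0.1508, mean risk 0.0718, recorded rate 0.8 × 0.14 + 0.2 × 0.0718 = 12.64%.
- Difference: 9.07 points, and false non-inferiority is 8.5%.

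Ranges over the three shapes:

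| Loss, mesh/control | Timing of the mesh excess | Loss spread | Loss in year 1 |
|---|---|---|---|
| 20% / 20% | all before any loss | 5.2–5.3% | 5.2–5.3% |
| 20% / 20% | a quarter follows control timing, rest before loss | 5.4–6.0% | 5.8–6.6% |
| 20% / 20% | half follows control timing, rest before loss | 5.7–6.8% | 6.4–8.2% |
| 20% / 20% | same pattern in both arms | 6.2–8.5% | 7.5–12.1% |
| 10% / 10% | same pattern in both arms | 5.7–6.6% | 6.2–8.0% |
| 25% / 15% | same pattern in both arms | 7.4–13.0% | not shown |

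In the fourth row the difference is understated by 0.3–0.9 points (spread) or 0.7–1.6 points (year 1). If all loss precedes a late quarter of the excess, the figure is 6.7–7.0%. With the same pattern in both arms and lower mesh loss, the inflation disappears or reverses: 15% / 25% gives 5.2–5.4%, and 10% / 20% gives 4.3–4.9%. Break-even control loss was 1.64–1.72 times mesh loss in every case run.

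The absolute numbers are small. At 14% risk and 20% loss, about 1–3 events per arm go unseen with spread loss and 2–5 with year-1 loss.

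**Does the alternative restore the error rate?** Unstratified, with event and loss times uniform over 36 months, false non-inferiority is 8.8% crude against 5.1% with Kaplan-Meier and Greenwood variance at 20% / 20%, and 20.1% against 5.3% at 30% / 10%. With five strata in both analyses and constant hazard, it is 8.2% crude against 5.1%.

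**The case against.** The strongest reply is that the size depends on inputs the documents do not give. They state one 20% loss figure, not split by arm or by time, and no timing for serious events. In the milder cases the inflation is under one point, and if control loss is well above mesh loss the rule is conservative. That stands, and it makes the concern conditional.

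A second reply is that missing the Month 36 examination is not the same as losing serious-event data. Section 11.4.5 asks sites to "conduct as much of the visit as possible by phone (i.e., assess adverse events, risk factors, and analgesic intake"). Section 10.2.3 requires repeated contact attempts, and applies only after "the subject has missed two consecutive follow-up visits within a 12 month calendar period, the subject may be considered lost to follow-up". Table 21.7-1 keeps related serious events reportable through study end. These measures reduce the number of unseen events, and the 10% rows above allow for that. They do not change how a lost subject is scored.

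Three smaller points also stand. Major deviation is not defined, so the per-protocol set might drop some lost subjects; the ITT conclusion is unaffected. The sensitivity list in Section 12.3.8.2 is not expressly confined to efficacy, though that is its likelier reading. The synopsis defers to a Statistical Analysis Plan; if a separate text exists with a safety rule, it should be checked.

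Finally, events over all treated subjects is a common safety summary, and a tipping-point analysis alone would address informative loss. But it would leave a co-primary estimate that treats unobserved time as event-free.

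**Conclusion.** The concern holds. In ITT, the written rule scores every subject lost without a recorded event as event-free to 36 months, and no safety missing-data method is stated. This follows from the text and needs no assumption.

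Whether it inflates error depends on two conditions: mesh loss about equal to or above control loss, and some of the mesh excess falling after loss. Under equal 20% loss, the cases examined run from no inflation (5.2–5.3%) to 12.1%, and to 14.7% in the limit where every lost subject's event falls after she leaves. These figures assume 24% against 14%, 207 per arm, an unstratified interval and non-informative loss. No error rate was computed for the 12-month safety test, which uses the same counting. The point should be fixed before the final analysis.

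**What to change.** In each propensity stratum, estimate the 36-month risk of a first endpoint event by Kaplan-Meier, or by cumulative incidence with unrelated death as a competing event, and state which. Use the Greenwood (or corresponding) variance as V_j in Section 12.2.3. Keep the n_j/n weights and the 10-point margin.

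State one censoring rule that treats events and event-free time alike. For example, for a subject who leaves early, stop both at the last scheduled visit or phone contact at which adverse events were assessed, not at the date loss is declared. Events reported later in subjects who never return go into sensitivity analyses. The rule matters: counting events to loss but event-free time only to the last visit overstated risk by 0.3–0.7 points in mesh and 0.1–0.4 in control.

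Use the same estimator for the 12-month safety test. Keep the crude ITT proportion, with all reported events, as a sensitivity analysis. Add a safety tipping-point analysis by arm, because censoring assumes non-informative loss.

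The cost is SAP wording and standard procedures. Adverse-event onset date is already on the case report form (Table 21.7-1). The documents do not say that a last adverse-event assessment date is captured, so confirm it or derive it from visit and contact dates. At 14% in both arms, equal 20% loss and constant hazard, the interval half-width grows from about 5.2–5.4 to 5.9–6.2 points and power falls from 92–94% to about 85–87%, still above the planned 80%. Where events come early and loss is spread, the gain is small: 6.2% crude against about 5.4–5.6%.
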